3.1.4. Response Assessments

A bone marrow assessment will be performed on Cycle 3 Day 1 to document initial response. Bone marrow assessments will be performed every 3 cycles (approximately every 12 weeks) from Cycle 6 until Cycle 12 (Day 1 of C6, C9, C12), and then every 6 cycles (C18, C24, etc.) thereafter. If an initial response (CR, CRh, PR, or CI) is achieved on or after C12, a repeat bone marrow assessment will be performed 12 weeks after the initial documented response to confirm response per modified IWG-MRT-ECNM response criteria. Changes in liver and spleen size will be assessed by MRI and palpation. A computed tomography scan may be used if MRI cannot be performed. Skeletal imaging is required at Screening for all subjects to assess for baseline lytic lesions and/or pathologic fractures. Changes in the size of bony lesions will be assessed with skeletal imaging. Refer to [Section 6.15](#) for further information regarding disease assessments.

[figure not shown]
3.1.5. Safety Assessments

Safety will be assessed by AEs, physical examinations, vital signs, hematology and chemistry laboratories, and electrocardiograms (ECGs). AEs will be coded using the latest Medical Dictionary for Regulatory Activities (MedDRA) version available at the time of database creation and will be graded according to the National Cancer Institute Common Terminology Criteria for Adverse Events (NCI CTCAE) version 5.0 or higher.

3.1.6. Pharmacokinetic and Pharmacodynamic Assessments

Blood samples will be collected for determination of bezuclastinib PK. Predose PK blood samples will be collected within 30 minutes before initial daily dosing. Blood and bone marrow will be collected for analysis of the clinical and pharmacodynamic effects of bezuclastinib.

Figure 1: Study Schematic

*Of the 28 subjects randomized in Part 1, 4 subjects may be included who are non-evaluable per modified IWG-MRT-ECNM response criteria. In addition to the ~55 subjects who are evaluable per modified IWG-MRT-ECNM response criteria in Part 2 Stage 2, up to an additional ~15 subjects who are non-evaluable per modified IWG-MRT-ECNM response criteria may participate.

Abbreviations: C=cycle, D=day, IWG-MRT-ECNM=International Working Group-Myeloproliferative Neoplasms Research and Treatment European Competence Network on Mastocytosis, QD=once daily.

Note: The study will continue until all subjects have completed at least 2 years of follow-up for overall survival, withdrawn from study participation, been lost to follow-up, or died, whichever occurs first.

4. STUDY POPULATION

4.1. INCLUSION CRITERIA

Consideration should be given to the suitability of available alternative therapies (eg, midostaurin, avapritinib) prior to study enrollment. Subjects must meet all of the following inclusion criteria:

1. Diagnosed with 1 of the following advanced mastocytosis diagnoses based on WHO diagnostic criteria ([Appendix A](#)):
 - ASM
 - SM-AHN (The associated hematologic neoplasm must be myeloid, with the following diagnoses excluded from study entry: acute myeloid leukemia, myelodysplastic syndrome that is very high- or high-risk as defined by the Revised International Prognostic Scoring System for Myelodysplastic Syndromes, Philadelphia Chromosome positive malignancies, and patients with $\geq 10\%$ blast cells in bone marrow)
 - MCL
2. Measurable disease according to modified IWG-MRT-ECNM consensus eligibility and response criteria for CI ([Appendix C](#))

NOTE: Diagnosis and evidence of measurable disease (including at least 1 measurable C-finding per modified IWG-MRT-ECNM response criteria for patients with ASM and SM-AHN [patients with MCL do not require a C-finding]) must be confirmed by the EC prior to the first dose of study drug.

NOTE: Up to 4 subjects in Part 1 and up to an additional 15 subjects in Part 2 Stage 2 who have AdvSM and are non-evaluable per modified IWG-MRT-ECNM response criteria based on lack of evaluable organ damage per modified IWG-MRT-ECNM may be enrolled.

3. Able to provide written informed consent
4. Able and willing to commit to study assessments and visit schedule
5. Age ≥ 18 years of age
6. Eastern Cooperative Oncology Group (ECOG) Performance Status 0 to 3
7. Have clinically acceptable laboratory screening results (clinical chemistry, hematology) within certain limits specified below:
 - a. Absolute neutrophil count $> 500/\mu\text{L}$ (subjects enrolled in Part 1 only)
 - b. Platelet count $\geq 50,000/\mu\text{L}$ prior to the first dose of study drug
 - c. AST and alanine aminotransferase (ALT) $\leq 2.5 \times$ upper limit of normal (ULN) or $\leq 5 \times$ ULN if there is liver involvement by AdvSM

- d. Direct bilirubin $\leq 1.5 \times \text{ULN}$; if related to AdvSM may be $\leq 3 \times \text{ULN}$
 - e. Calculated creatinine clearance (Cockcroft-Gault) ≥ 40 mL/min
 - f. Serum tryptase ≥ 20 ng/mL
8. For women of childbearing potential (WOCBP; defined as physiologically and anatomically capable of becoming pregnant), confirmation of a negative serum pregnancy test and agreement to the use of a highly effective method of contraception with or without a barrier contraception method (in accordance with country-specific guidance) during the study treatment period and for 6 weeks after the last dose of bezuclastinib; for male subjects, agreement to use effective barrier contraception (ie, condoms) during the study treatment period and for 6 weeks after the last dose of bezuclastinib
9. Able to swallow pills

4.2. EXCLUSION CRITERIA

Subjects will not be eligible for inclusion in this study if any of the following criteria apply:

1. Persistent toxicity from previous therapy for AdvSM that has not resolved to \leq Grade 1.
2. Patients presenting with an associated hematologic neoplasm who require immediate antineoplastic therapy.
3. Clinically significant cardiac disease, defined by any of the following:
 - a. Uncontrolled or untreated cardiac arrhythmias
 - b. Congenital long QT syndrome or concomitant medications known to prolong the QT interval except those required for infections that carry a low risk of QTc prolongation.
 - c. A marked baseline prolongation of QT/QTc interval (eg, repeated demonstration of a QTcF [QT corrected using Fridericia's formula] interval > 480 msec).
 - d. History of clinically significant cardiac disease or congestive heart failure $>$ New York Heart Association Class II. (Patients must not have unstable angina [anginal symptoms at rest] or new-onset angina within the last 3 months or myocardial infarction within the past 6 months.)
 - e. Arterial or venous thrombotic or embolic events such as cerebrovascular accident (including transient ischemic attacks), deep vein thrombosis, or pulmonary embolism within the 6 months before study drug initiation (except for adequately treated catheter-related venous thrombosis occurring more than 1 month before the first dose of study drug).
4. Known positivity for the *FIP1L1-PDGFR*A fusion (except for patients who demonstrated relapse or disease progression on prior imatinib therapy). Patients with eosinophilia (eosinophil count $> 1.5 \times 10^9/\text{L}$) who do not have a detectable *KIT* D816V mutation must provide documentation of the lack of a PDGFR A fusion mutation by fluorescence in situ hybridization or polymerase chain reaction prior to enrollment.

5. Any other concurrent severe known disease or concurrent severe and/or uncontrolled medical condition (eg, uncontrolled diabetes or active uncontrolled infection), either of which could compromise participation in the study.
6. Seropositive for human immunodeficiency virus (HIV) 1 or 2, positive for hepatitis B surface antigen, or positive for hepatitis C virus (HCV) antibody. (Subjects with a positive HCV antibody may be eligible if HCV RNA is undetectable on a quantitative HCV RNA assay, following discussion with the Medical Monitor.)
7. Active, uncontrolled, systemic bacterial, fungal, or viral infections at Screening.
NOTE: Oral antibiotics for a controlled infection are permitted with Medical Monitor approval. Patients on antimicrobial, antifungal, or antiviral prophylaxis are not specifically excluded if all other inclusion/exclusion criteria are met.
8. History of clinically significant bleeding event within 30 days before the first dose of study drug or need for therapeutic anticoagulation on study.
9. Diagnosed with or treated for malignancy other than the disease under study within the prior 3 years before enrollment or expected to need treatment for an active malignancy. (The following are allowed within 3 years of study enrollment if the subject has received definitive local therapy [eg, surgical excision, external beam radiation, or other local therapy with curative intent]: non-melanoma skin cancers, localized prostate cancer, or carcinoma in situ.)
10. Any condition that could hamper compliance with the study protocol in the judgment of the Investigator.
11. Pregnant or currently breastfeeding.
12. Received any cytoreductive therapy (including midostaurin and other tyrosine kinase inhibitors, hydroxyurea, azacitidine) or any investigational agent less than 14 days, and for cladribine, interferon alpha, pegylated interferon, and any antibody therapy (eg, brentuximab vedotin) less than 28 days, before obtaining screening bone marrow biopsy for this study.
13. Received hematopoietic growth factor (eg, granulocyte colony-stimulating factor [G-CSF], granulocyte-macrophage colony-stimulating factor) support within 14 days before the first dose of study drug.
14. Received strong CYP3A4 inhibitors or inducers within 14 days or 5 drug half-lives, whichever is longer, before the first dose of study drug or the need to continue treatment with strong CYP3A4 inhibitors or inducers during the study (Refer to [Appendix H](#)).
15. Need for treatment with steroids (>10 mg prednisone or equivalent per day). Subjects on a stable dose of prednisone or equivalent that is ≤10 mg per day are eligible.
16. Known hypersensitivity to bezuclastinib or any of its components.

4.3. SUBJECT WITHDRAWAL CRITERIA

4.3.1. Treatment Discontinuation for Individual Subjects

Treatment discontinuation is defined as an instance in which a subject permanently stops receiving study drug and does not restart drug. Subjects who experience a TEAE that is assessed as at least possibly related to study drug and require a dose interruption of more than 28 days must permanently discontinue treatment with bezuclastinib. A subject should be discontinued from study treatment if, in the opinion of the Investigator or Sponsor, it is medically necessary to do so, or if it is the wish of the subject. A subject who becomes eligible for hematopoietic stem cell transplantation (HSCT) and for whom HSCT is the most appropriate therapeutic option should discontinue treatment and receive HSCT at the discretion of the Investigator.

A subject must discontinue study treatment for:

- Protocol-specified documented disease progression
- Investigator decision
- Subject withdrawal of consent
- Development of an AE, that in the opinion of the Investigator, would render continued participation harmful to the subject
- Subject pregnancy
- Lost to follow up (ie, inability by the Investigator to contact and/or effectively monitor the subject)
- Termination of study by Sponsor
- Enrollment in another therapeutic study
- Receiving a non-protocol-approved treatment plan for treatment of the subject's AdvSM

The Sponsor is to be immediately notified if a subject discontinues study treatment for any reason. The reason for treatment discontinuation must be documented on the appropriate electronic case report form (eCRF). Noncompliance with the protocol medication/treatments and/or required follow-up, as judged by the Investigator, may result in discontinuation of study drug.

4.3.2. Study Discontinuation for Individual Subjects

Subjects enrolled in this study may withdraw from the study at any time without penalty or loss of future medical care or any other benefits to which they are otherwise entitled. Subjects will be withdrawn from the study for any of the following reasons:

- Subject is lost to follow-up (ie, inability by the Investigator to contact and/or effectively monitor the subject)
- Subject withdrawal of consent

- Subject death
- Investigator decision
- Termination of study by Sponsor
- Adverse event
- Enrollment in another therapeutic study

The Sponsor is to be immediately notified if a subject is withdrawn from the study for any reason. The reason for study withdrawal must be documented on the appropriate eCRF.

The Sponsor must be notified if the Investigator identifies a subject who did not meet enrollment criteria but was inadvertently enrolled. Similarly, if the Sponsor identifies a subject who did not meet enrollment criteria but was inadvertently enrolled, the Investigator will be notified. A discussion must occur between the Medical Monitor and the Investigator to determine whether it is medically appropriate for a subject to continue in the study, with or without the study treatment regimen. The Investigator must then obtain documented approval from the Medical Monitor if the subject is to be allowed to continue in the study with or without the study treatment regimen.

4.4. STUDY STOPPING RULES

The IDMC will be convened to determine whether the study should be stopped or enrollment should be paused or discontinued for a particular dose cohort based on any of the following safety events:

- ≥ 2 subjects discontinuing treatment due to a treatment-related toxicity in a particular dose cohort (Part 1 or Part 2 Stage 1).
- Non-hematologic treatment-related Grade 4 toxicity that occurs within 30 days of initiating treatment.
- Treatment-related death that occurs within 30 days of initial dosing will result in enrollment pause across all dose cohorts until the IDMC has convened.

Additionally, the SSC will meet regularly to assess the totality of the data and assess response rate to determine whether the study should be stopped or enrollment should be paused or discontinued for a particular dose cohort based on lack of treatment effect under the following circumstance:

- ≤ 1 of 5 subjects in a given dose cohort with stable disease or better after 6 cycles of treatment (Part 1).

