3.1.1. Study Governance

An EC will review subject eligibility and will approve subject enrollment during the Screening Period. The clinical history and pathology must be centrally reviewed before a subject is enrolled. The EC will consist of a pathologist and at least 1 clinician who is skilled in the diagnosis and treatment of mastocytosis.

A Study Steering Committee (SSC) will be responsible for advising the Sponsor throughout Part 1 and Part 2 of the study. The SSC will be composed of Lead Principal Investigators and the Study Medical Monitor and will be responsible for assisting the Sponsor with protocol development, amendments, study conduct, and interpretation of data. The selected dose for Part 2 Stage 2 based on available data from Part 1 and Part 2 Stage 1 will be reviewed and confirmed by the SSC before the selected dose is administered in Part 2 Stage 2.

A Central Response Review Committee (CRRC) will retrospectively review disease-specific eligibility criteria and the presence of 1 or more baseline modified IWG-MRT-ECNM findings. The CRRC will review all available data to assess response per the modified IWG-MRT-ECNM response criteria. The CRRC will consist of an independent pathologist, 1 independent clinician, and at least 2 clinicians who are skilled in the treatment of mastocytosis.

An Independent Data Monitoring Committee (IDMC) will aid in the monitoring of accumulating study data to ensure the ongoing safety of trial participants and will play a role in confirming the recommendations and decisions made by the Sponsor across bezuclastinib clinical trials. The IDMC membership will be composed of external medical experts with relevant clinical experience. The IDMC will review the available data and recommendation from the SSC regarding the optimal dose selected in Part 2 Stage 1 for Part 2 Stage 2. The IDMC will have the right to recommend stopping the study at any time due to concerns for the safety of the subjects.

Charters will govern each of these committees as appropriate.

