3.1.2. Part 1: Dose Optimization

In Part 1 of the study, approximately 28 subjects will be randomized to 1 of 4 dose cohorts of bezuclastinib (Formulation A), including up to 4 subjects who are non-evaluable per modified IWG-MRT-ECNM response criteria based on lack of evaluable organ damage per modified IWG-MRT-ECNM criteria. Subjects will be randomized in a 1:1:1:1 (50 mg BID:100 mg

BID:200 mg BID:400 mg QD) manner. Randomization will be stratified by evaluability per modified IWG-MRT-ECNM response criteria (ie, evaluable vs non-evaluable).

Table 4: Single-Agent Dose Optimization Cohort

	Bezuclastinib Dose × 28-Day Cycles			
	Dose Cohort 1	Dose Cohort 2	Dose Cohort 3	Dose Cohort 4
Initial Dose	50 mg BID	100 mg BID	200 mg BID	400 mg QD
Total Daily Dose	100 mg	200 mg	400 mg	400 mg

Abbreviations: BID=twice a day; QD=once daily.

Bezuclastinib Formulation A will be administered orally as a single agent and should be taken with food and water. Each 28-day period is 1 cycle. Subjects will receive bezuclastinib at their assigned dose cohort until confirmed disease progression, intolerable toxicity, Investigator decision, withdrawal of consent, or other protocol-specified reason for discontinuation of study drug, whichever occurs first. Once the optimal dose level of bezuclastinib Formulation B is confirmed in Part 2 Stage 1, subjects receiving Formulation A may be transitioned to receive Formulation B. Additional blood samples for PK may be collected following the transition from Formulation A to Formulation B.

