3.1.3. Part 2: Dose Confirmation and Expansion

Part 2 will be conducted with a 2-stage design: Stage 1 will confirm the optimal dose of bezuclastinib Formulation B, and Stage 2 will consist of an expansion period.

In Stage 1, approximately 20 subjects who are evaluable per modified IWG-MRT-ECNM response criteria will be randomized 1:1 to receive 150 mg QD or 300 mg QD of bezuclastinib Formulation B. Randomization will be stratified by prior treatment of TKI (ie, yes vs no). Based on available data from Part 1, 150 mg QD of bezuclastinib Formulation B is expected to provide clinical activity with acceptable safety and tolerability. A higher dose level of bezuclastinib, 300 mg QD, will also be explored to determine if an increased dose results in increased clinical activity with acceptable safety and tolerability. The totality of clinical data from Part 1 and Part 2 Stage 1 will be used to confirm the optimal Formulation B dose of bezuclastinib in subjects with AdvSM. Subjects in Part 2 Stage 1 may have their dose adjusted once the optimal dose of bezuclastinib Formulation B is confirmed.

Once approximately 20 subjects have been enrolled in Part 2 Stage 1, enrollment may continue until the dose for Part 2 Stage 2 is confirmed. Following enrollment of 20 subjects in Part 2 Stage 1 and prior to analysis of Part 2 Stage 2 data, enrolled subjects will receive either 150 mg and/or 300 mg based on ongoing review of available data and following IDMC approval. Of the additional subjects who may be enrolled, those who receive the dose selected for Part 2 Stage 2 will contribute to the Stage 2 analysis population.

In Stage 2, approximately 55 subjects who are evaluable per modified IWG-MRT-ECNM response criteria will be enrolled to receive bezuclastinib Formulation B at the selected optimal

dose. Up to approximately 15 additional subjects who are non-evaluable per modified IWG-MRT-ECNM response criteria based on lack of evaluable organ damage per modified IWG-MRT-ECNM criteria may be enrolled.

To ensure the study population reflects the general AdvSM patient population, enrollment of the SM-AHN subtype will be capped at approximately 80% ([Jawhar et al, 2019](#)).

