Anemia, neutropenia, thrombocytopenia (a)	Grade 4 anemia for ≥7 days Grade 4 neutropenia for ≥7 days, or Grade 3 or worse neutropenia associated with bacterial or fungal infection requiring systemic therapy Febrile neutropenia (any grade) Grade 4 thrombocytopenia for ≥7 days, or Grade 3 or worse thrombocytopenia associated with bleeding	Hold bezuclastinib until resolved to ≤Grade 1 or baseline. If recovered to ≤Grade 1 or baseline in ≤28 days, reduce by 1 dose level. If not recovered to ≤Grade 1 or baseline after 28 days, discontinue study drug.

Table 6: Dose Modification Criteria for TEAEs At Least Possibly Related to Bezuclastinib

TEAE	Criteria or CTCAE v5.0 Grade	Dose Modification
ECG QT prolonged	Grade 3: >500 msec or >60 msec increase from baseline (b)	Hold bezuclastinib until QTc ≤500 msec (≤Grade 2); then reduce by 1 dose level If not recovered to ≤Grade 1 or baseline after 28 days, discontinue study drug.
	Grade 4: Torsade de pointes, polymorphic ventricular tachycardia, or signs/symptoms of serious arrhythmia	Permanently discontinue study drug.
Transaminase increases	ALT or AST >8×ULN ALT or AST >5×ULN for more than 2 weeks ALT or AST >3×ULN and TBL >2×ULN or INR >1.5 ALT or AST >3×ULN with the appearance of fatigue, nausea, vomiting, right upper quadrant pain or tenderness, fever, rash, and/or eosinophilia (>5%)	Consider the possibility of drug-induced liver injury. If drug-induced liver injury is suspected, permanently discontinue study drug if it is in the best interest of the subject.
Other non-hematological toxicity (excluding Grade 3 nausea, vomiting, or diarrhea lasting ≤72 hours with adequate prophylactic and supportive care), including clinically significant non-hematologic laboratory parameters (excluding elevations in alkaline phosphatase)	Grade 3	Hold bezuclastinib until resolved to ≤Grade 1 or baseline. If recovered to ≤Grade 1 or baseline in ≤28 days, reduce by 1 dose level. If not recovered to ≤Grade 1 or baseline after 28 days, discontinue study drug.
	Grade 4	Permanently discontinue study drug unless considered unrelated to treatment.

Abbreviations: AE=adverse event, ALT=alanine transaminase, AST=aminotransferase, CTCAE=National Cancer Institute Common Terminology for Adverse Events, ECG=electrocardiogram, MCL=mast cell leukemia, QTc=corrected QT interval, TBL=total bilirubin, TEAE=treatment-emergent adverse event, ULN=upper limit of normal.

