7.2. PROCEDURES FOR RECORDING AND REPORTING ADVERSE EVENTS

7.2.1. Adverse Event Recording

Each subject must be carefully monitored for the development of any AEs. This information should be obtained in the form of non-leading questions (eg, “How are you feeling?”) and from signs and symptoms detected during each assessment, observations of study personnel, and spontaneous reports from subjects.

After the ICF is signed, site personnel will note any change in the condition(s) and the occurrence and nature of any AEs. From the signing of the study informed consent form until the first dose of bezuclastinib, only SAEs and AEs considered related to on-protocol procedures will be collected. TEAEs will be recorded from the start of study treatment until 30 days after the last dose of study drug.

All AEs (serious and non-serious) will be monitored until resolved, stabilized, or returned to baseline status during study participation.

After receipt of any study drug, all AEs spontaneously reported by the subject and/or in response to an open question from the study personnel or revealed by observation will be recorded via eCRF.

Laboratory abnormalities or other abnormal assessments (eg, physical examination findings, vital signs, ECGs) should only be recorded as AEs if clinically significant (ie, requiring medical or surgical intervention); abnormalities that lead to investigational therapy discontinuation, delay, or interruption; or abnormalities associated with clinical signs or symptoms.

Whenever possible, the clinical diagnosis, rather than the laboratory result or signs and symptoms, should be reported by the Investigator (eg, anemia vs decreased hematocrit) as 1 comprehensive event.

If a constellation of signs and/or symptoms cannot be medically characterized as a single diagnosis or syndrome at the time of reporting, each individual event should be recorded on the eCRF. If a diagnosis is subsequently established, all previously reported AEs should be replaced based on the single diagnosis.

The AE term should be reported in standard medical terminology when possible.

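### Section 4.4 closes the Grade 4 and treatment-related-death triggers 30 days after first dose, so Part 2 Stage 2 has no event-based trigger after a subject's Day 30

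*Protocol*

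**What the plan says.** Section 4.4 lists three safety events that convene the IDMC:

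- Discontinuations: two or more "subjects discontinuing treatment due to a treatment-related toxicity in a particular dose cohort (Part 1 or Part 2 Stage 1"). There is no time limit, but the rule is confined to those two segments of the study.
- Grade 4: "Non-hematologic treatment-related Grade 4 toxicity that occurs within 30 days of initiating treatment". There is no limit by part or stage.
- Death: "Treatment-related death that occurs within 30 days of initial dosing will result in enrollment pause across all dose cohorts until the IDMC has convened". This is the only automatic enrollment pause in the section.

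Sections 3.1.2 and 3.1.3 keep subjects on treatment until progression, intolerable toxicity or another listed reason. Section 7.2.1 sets the adverse-event period: "TEAEs will be recorded from the start of study treatment until 30 days after the last dose of study drug".

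Exposure may change well after first dose. Once the Formulation B dose is confirmed, Section 3.1.2 says "subjects receiving Formulation A may be transitioned to receive Formulation B". Section 3.1.3 says "Subjects in Part 2 Stage 1 may have their dose adjusted once the optimal dose of bezuclastinib Formulation B is confirmed".

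Outside the triggers, Section 3.1.1 has the IDMC help monitor accumulating data and adds: "The IDMC will have the right to recommend stopping the study at any time due to concerns for the safety of the subjects". Section 4.5 lets the sponsor end the study early, for example on observing an unexpected significant risk.

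**The concern.** The rules that oblige independent review apply only to each subject's first month of open-ended treatment. Section 4.4 does not leave this to another document: by fixing the window, it excludes a treatment-related death on Day 31.

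The gap matters most in Stage 2, the largest group, where the one trigger without a time limit does not apply. Enrollment there could continue after a late treatment-related death with no step in the protocol requiring the IDMC to meet. The clock also runs from first dose only, so a later change of formulation or dose opens no new window.

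**Working it through.** The protocol gives no error rate or operating characteristic for the stopping rules, so there is no stated figure to reproduce. The check has three steps.

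**1. Which triggers apply, and when (Section 4.4)**

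| Segment | Up to Day 30 from first dose | After Day 30 |
|---|---|---|
| Part 1 | Death, Grade 4, discontinuations | Discontinuations (two or more in a cohort) |
| Part 2 Stage 1 | Death, Grade 4, discontinuations | Discontinuations (two or more in a cohort) |
| Part 2 Stage 2 | Death, Grade 4 | None |

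A single late treatment-related death meets no trigger in any row. In Part 1 or Stage 1 it could at most count as one of the two discontinuations, if a death is read as a discontinuation. Subjects enrolled after the first 20 in Stage 1 have no clear row: Section 3.1.3 enrolls them before the dose is confirmed, but counts those on the selected dose in the Stage 2 analysis population.

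**2. Share of treatment time inside the window**

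Share = 30 / (28 × number of cycles).

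- 2 cycles: 30/56 = 53.6%
- 6 cycles: 30/168 = 17.9%
- 12 cycles: 30/336 = 8.9%
- 24 cycles: 30/672 = 4.5%

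Dose confirmation comes after the Stage 1 subjects have completed at least 2 cycles, that is 56 days (Section 1.3.3). Any switch or adjustment that follows is past Day 30 for the subjects reviewed.

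**3. Illustration of what the window can see in Stage 2**

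The protocol gives no event rate. Assume a per-subject risk p of a qualifying event over 12 cycles, a constant hazard, and all subjects treated for 12 cycles. The risk inside the window is w = 1 − (1 − p)^(30/336). The chance of at least one event among n subjects is 1 − (1 − p)^n at any time and 1 − (1 − w)^n inside the window.

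| Assumed p | n = 55, any time | n = 55, in window | n = 70, any time | n = 70, in window |
|---|---|---|---|---|
| 2% | 0.67 | 0.09 | 0.76 | 0.12 |
| 5% | 0.94 | 0.22 | 0.97 | 0.27 |
| 10% | 1.00 | 0.40 | 1.00 | 0.48 |

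A constant hazard may overstate the gap if toxicity comes early. Suppose instead that half of a 2% risk falls in the first 30 days. The chance of at least one event after Day 30 is then 1 − 0.99^55 = 0.42 with 55 subjects and 1 − 0.99^70 = 0.51 with 70.

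For a 10-subject Stage 1 arm, the chance of two or more events at any time is 0.02, 0.09 and 0.26 at p = 2%, 5% and 10%. If each event led to discontinuation, those pairs would meet the discontinuation trigger. The cover is real there, but it needs two events.

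**The case against.** The strongest reply is that oversight does not stop on Day 30. In Part 1 and Stage 1 the discontinuation trigger has no time limit. For other non-hematologic Grade 4 toxicity, Table 6 in Section 5.6 says "Permanently discontinue study drug unless considered unrelated to treatment", so two such late events in one cohort do convene the IDMC. A reader might infer that late events escape IDMC review altogether; the protocol does not support that. The cover is still partial. It needs two events, it is absent in Stage 2, and the transaminase row of Table 6 makes discontinuation conditional, so a late hepatic event need not count.

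Section 3.1.1 also gives the IDMC continuing monitoring and a right to recommend stopping. Section 7.2.4 requires SAEs to be reported within 24 hours, and Section 7.2.6.1 does the same for on-treatment deaths other than those from progression. This stands, and a charter that is not shown may add more. However, none of these provisions makes a late event oblige the IDMC to meet, and Section 4.5 is sponsor discretion.

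A reader might also infer a planned move to higher exposure. Both changes are optional, and their direction depends on the starting cohort and the selected dose. By nominal daily dose, the Part 1 cohorts start at 100, 200, 400 and 400 mg. A switch to 150 mg is an increase for one cohort and a decrease for three; a switch to 300 mg is an increase for two and a decrease for two. In Stage 1 the change could be from 150 to 300 mg or the reverse. Milligrams are not exposure here, because formulation and food conditions differ. The separate figures in Section 1.3.2 (a high-fat-meal effect and a maximum gain) do not give a dependable multiplier.

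Lastly, the adverse-event window governs data collection, so its mismatch with Section 4.4 is a design choice and not a contradiction. That is fair, and it limits the point to a recommendation.

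**Conclusion.** The point holds as a design weakness that should be corrected. After Day 30, Stage 2 has no event-based safety trigger, and no part has a trigger for a single treatment-related death. This follows from the text of Section 4.4 and needs no assumption.

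The time shares (8.9% of 12 cycles, 4.5% of 24) are plain arithmetic on treatment time. They are not the share of events caught, which depends on when toxicity occurs. The probabilities rest on assumed risks of 2% to 10% and an assumed event pattern, so they only illustrate the scale.

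That the window does not restart after a switch or dose adjustment is a secondary point: those changes are permitted, not certain, and may raise or lower exposure.

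**What to change.** In Section 4.4, apply the treatment-related-death trigger for convening the IDMC over the protocol's own adverse-event window, from first dose to 30 days after the last dose, in all parts including Stage 2. State whether the automatic enrollment pause goes with it.

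Reconcile Section 4.4 with Sections 3.1.2 and 3.1.3 by stating how the Grade 4 and discontinuation triggers apply:

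- in Stage 2;
- to subjects enrolled after the first 20 in Stage 1;
- after a formulation switch or dose change, including the cohort in which such a subject is counted.

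Any thresholds or windows for these are for the sponsor and the IDMC to set. The cost is amendment and charter wording, and possibly a few extra ad hoc IDMC meetings and short enrollment pauses.
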